- f For participants continuing in the study, the common EOS visit will be done when the prespecified number of events for 6-month CDP is expected to be reached. The timing and window of this visit will be communicated to sites.
- *g* Any disease-modifying therapy for MS taken at any time prior to signing the informed consent needs to be reported in the eCRF; other prior medications will be reported for the period of 6 months prior to signing the ICF.
- *h* Complete physical examination due at screening, baseline, yearly (M12, M24, M36, M48) and at EOS; brief physical examination is sufficient for the rest of the visits (complete and brief physical examinations will include neurological examination and collection of the following vital signs: arterial blood pressure, heart rate, temperature).
- *i* To be performed at screening for all participants. Tuberculosis examination will be repeated based on clinical judgment, borderline results, or clinical suspicion of TB infection. For further details, refer to E 01. Screening tests for TB are described in Appendix 2 (Section 10.2).
- *j* ECG and 30 second rhythm strips will be obtained locally.
- k Hematology (platelet count, RBC count, hemoglobin, hematocrit, MCV, MCH, reticulocytes, WBC count with differential: neutrophils, lymphocytes, eosinophils, basophils). Biochemistry (blood urea nitrogen [BUN], creatinine, glucose, sodium, potassium, bicarbonate, calcium, liver function tests [AST, ALT, ALP, albumin, total and direct bilirubin], total protein; creatine phosphokinase. Lipase will be tested at the Screening Visit, then quarterly. Monthly visits (M1, M2, M4, and M5) will include hematology and full liver panel only. Additional safety assessments can be performed if required by local regulations. Such testing shall be performed at local laboratories.

Note: a one-time retest at screening may be performed if laboratory test abnormality is considered temporary. Additional safety assessments can be performed if required by local regulations; such testing shall be performed locally whenever possible. Additional visits may be added if required by local regulations.

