- I At intermediate timepoints (W2, W3, W5, W6, W7, W9, W10, W11, M7, M8, M10, and M11), only liver function tests will be collected (AST, ALT, albumin, alkaline phosphatase, total and direct bilirubin, total protein) and creatine phosphokinase); these can be performed at central laboratory (preferred, as on-site visits or home nursing as applicable for the site) or at local laboratory; a window of ±3 days is permitted for weekly liver function test (LFT) timepoints and ±7 days for the other timepoints. Additional information is provided in the Study Manual. For participants switching to open-label treatment, please refer to Section 6.6.1.
- *m* At screening, perform the serum ß-hCG pregnancy test at the central laboratory. At randomization and other scheduled visits during the study, urine pregnancy tests should be performed. At randomization, a pregnancy test should be performed prior to the first dose of IMP. Additional serum or urine pregnancy tests may be performed, as determined necessary by the Investigator or required by local regulation, to establish the absence of pregnancy at any time during the participant's participation in the study. Communication by phone of the result of a pregnancy test performed at home to the site is allowed. See also Appendix 4 (Section 10.4).
- *n* Only in female participants, if needed to establish menopausal status.
- o The SDMT and CVLT-II will be performed in all participants. If for some reason, CVLT-II is not available at a given site due to reasons such as lack of translation, local certification, etc., then only the SDMT will be assessed for that participant.
- *p* A subset of sites that have 3T MRI capacity will perform additional sequences (eg, SWI). Further details will be defined in a central MRI manual.
- *q* A visit window of ±21 days is acceptable for MRIs performed after D1. For systemic corticosteroids and adrenocorticotropic hormone, 1-month wash-out required prior to the MRI scans. The screening MRI scan should be performed as close as possible before the start of IMP. As much as possible, the MRI scan should be performed during the screening period only after it has been established that the participant meets all inclusion and no exclusion criteria.
- r A noninvasive activity monitor (actigraphy) may be optionally implemented by the Sponsor in a subset of participants during the course of the study if results from pilot assessment demonstrate feasibility.

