6.6.1 Open-label treatment

If a participant achieves the primary endpoint (6-month CDP), they may, in conjunction with the Treating Investigator, choose to receive one of the following:

- 1. To switch to open-label SAR442168 treatment; OR
- 2. To switch to a non-study treatment approved for NRSPMS in their respective country. In this case, the participant will permanently discontinue the IMP and will be encouraged to remain in the study for planned clinical visits (see Section 7.1.1) until common study end.

In case the participant switches to open-label SAR442168 treatment, he/she will need to be monitored for liver function tests after the first open-label dose at Weeks 2, 3, 4, 5, 6, 7, 8, 9, 10, 11, and 12, and then monthly for the next 9 months. After that, the schedule visits timepoints per SoA will be resumed (ie, every 3 months), until the common study end. Whenever a timepoint will coincide with a scheduled visit as per SoA (Section 1.3), the full scheduled visit assessments will be performed instead of the liver monitoring testing alone.

For participants achieving 6-month CDP, the Investigator must ensure that the participant does not meet any of the following criteria prior to the switch to open-label SAR442168 treatment:

• Current alcohol intake >2 drinks per day for men and >1 drink per day for women (1 drink = approximately 14 grams of alcohol = 350 mL beer = 140 mL wine = 40 mL of spirits).

- Acute liver disease, cirrhosis, chronic liver disease (unless considered stable for >6 months).
- Confirmed ALT >1.5 × ULN OR AST >1.5 × ULN OR ALP >2 × ULN (unless caused by non-liver-related disorder or explained by a stable chronic liver disorder) OR total bilirubin >1.5 × ULN (unless due to Gilbert syndrome or non-liver-related disorder).

Liver function tests will be performed for all participants prior to the start of open-label treatment.

Should the participant and Investigator opt for the provision of open-label medicine, they will remain blinded to the original treatment assignment.

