8 STUDY ASSESSMENTS AND PROCEDURES

- Study procedures and their timing are summarized in the SoA (Section 1.3). Protocol waivers or exemptions are not allowed.
- Adherence to the study design requirements, including those specified in the SoA (Section 1.3), is essential and required for study conduct.
- All screening evaluations must be completed and reviewed to confirm that potential participants meet all eligibility criteria. The Investigator will maintain a screening log to record details of all participants screened and to confirm eligibility or record reasons for screening failure, as applicable.
- Procedures conducted as part of the participant's routine clinical management (eg, blood count) and obtained before signing of the ICF may be utilized for screening or baseline purposes provided the procedures met the protocol-specified criteria and were performed within the time frame defined in the SoA. Such assessments will be recorded on the designated field in the eCRF.
- Blood sampling details including volume for all laboratory assessments will be provided in the laboratory manual, and the informed consent form. Repeat or unscheduled samples may be taken for safety reasons or for technical issues with the samples.
- In exceptional cases, under regional or national emergencies (eg, natural disaster, epidemic disease, terrorist attack), onsite visits may be replaced with telephone/remote visits. For example, participant interviews for medical history/prior medications could be performed by phone, local safety labs and some efficacy assessments could be performed off-site/at the participant's home (eg, home nursing) if agreed by the participant and permissible per local regulations. In such circumstances, the visit window may be expanded, if needed (eg, ±14 days for quarterly visits).

For a regional or national emergency declared by a governmental agency, contingency measures are included in Section 10.10, Appendix 10: Contingency measures for a regional or national emergency that is declared by a governmental agency.

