10.6 APPENDIX 6: LIVER AND OTHER SAFETY: ACTIONS AND FOLLOW-UP ASSESSMENTS

These actions are required for ALT increase and thrombocytopenia events ONLY. For all other safety events described, these are suggested per the Investigator's medical judgement.

[figure not shown]

- 3. **INFORM** the local monitor
- 4. **INVESTIGATE** previous treatments particularly long-term, even a long time ago, exposure to toxic agents, e.g., benzene, X-rays, etc.
- 5. **PERFORM** and collect the following investigations (results):
 - RBC and platelet counts, Absolute Neutrophil Count (ANC)
 - Infectious serologies to be performed locally, according to clinical symptoms / medical history
- 6. **DECISION** for bone marrow aspiration: to be taken in specialized unit
- 7. COLLECT/STORE one sample following handling procedures described in PK sections (for studies with PK sampling)
- 8. MONITOR the leukocyte count 3 times per week for at least one week, then twice a month until it returns to normal

* For individuals of African descent, the relevant value of concern is <1000/mm³

Neutropenia is to be recorded as an AE only if at least 1 of the criteria listed in the general guidelines for reporting AEs in Appendix 3 (Section 10.3) is met.

THROMBOCYTOPENIA

Abbreviations: aPTT: activated partial thromboplastin time; EDTA: Ethylenediaminetetraacetic acid; INR: international normalized ratio; PK: pharmacokinetic; PT: prothrombin time

[figure not shown]
Thrombocytopenia is to be recorded as an AE only if at least 1 of the criteria listed in the general guidelines for reporting AEs in Appendix 3 (Section 10.3) is met.

LIVER FUNCTION TEST MONITORING ADDITIONAL GUIDANCE:

To allow timely review for these data, please enter the date of collection for the central lab and the date of collection and the results for the local lab in the eCRF within 24 hours of their availability.

- 1. If 1 LFT monitoring timepoint is missed, the study site should:
 - Reach out to the study participant as soon as possible to schedule an alternative timepoint as soon as possible and prior to the next scheduled timepoint.
 - Retrain the study participant on the LFT monitoring rationale and requirements and inform the study participant that IMP will need to be interrupted if LFTs cannot be monitored as required.
- 2. If 2 consecutive LFTs timepoints are missed, the site should:

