 - Collect and store one PK sample following the instructions in the central laboratory manual;
 - Perform-hepatobiliary imaging (ultrasonography or other imaging investigations is required);
 - Consider DNA test for Gilbert's disease if clinically indicated;
 - Recommend consulting a hepatologist (mandatory if ALT >8 x ULN or is associated with elevated bilirubin);
 - Discuss with the hepatologist the clinical indication for potential liver biopsy (strongly recommended if the participant meets Hy's law criteria or has ALT >20 x ULN) and/or initiation of treatment with steroids;
 - Consider patient hospitalization if INR >2 (or PT <50%) and/or central nervous system disturbances suggesting hepatic encephalopathy.
- MONITOR LFTs after discontinuation of IMP:
 - Monitor closely (every 2-3 days) until ALT is down-trending, then weekly until <1.5 x ULN, and then at every scheduled visit;
 - This frequent LFT monitoring may be done through central or local lab, or via home visit (depending on the Investigator's assessment and/or local regulatory requirements).
- RECHALLENGE: Re-initiation of the study drug can only be considered after discussion with the Sponsor's Medical Monitor once the ALT/AST decreases to <1.5 x ULN, and there is no clinical contraindication. Rechallenge is not permitted for the following participants unless a clear non-DILI etiology is identified:
 - ALT >8 x ULN
 - ALT >5 x ULN for greater than two weeks
 - ALT >3 x ULN and total bilirubin >1 x ULN
 - In case it is agreed to re-start the study drug, it is recommended that ALT/AST be assessed per protocol schedule of assessments for the first 6 months of the treatment period.
 - The occurrence of new elevation to >3 x ULN for the ALT/AST values will lead to permanent discontinuation of the study drug.

ALT, alanine aminotransferase; AST, aspartate aminotransferase; CMV, cytomegalovirus; CPK, creatine phosphokinase; CRF, case report form; EBV, Epstein-Barr virus; GGT, gamma glutamyl transferase; HAV, hepatitis A virus; HBV, hepatitis B virus; HCV, hepatitis C virus; HEV, hepatitis E virus; IgG, immunoglobulin G; IgM, immunoglobulin M; IMP, investigational medicinal product; INR, international normalized ratio; LFT, liver function test; LKM, liver-kidney microsomal antibody; PT, prothrombin time; ULN, upper limit of normal.

[figure not shown]
INCREASE IN SERUM CREATININE in patients with normal baseline (creatininemia between 45 µmol/L and 84 µmol/L)

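### After a restart following an ALT event, intensified liver testing is only recommended and is not counted from the restart dose, so for restarts from Month 3 the next required blood draw can be 4 to 12 weeks away

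*Protocol*

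**What the plan says.** **Restart after an ALT event.** In the rechallenge item of Appendix 6 (Section 10.6), restart can be considered once ALT/AST is below 1.5 x ULN, after discussion with the Medical Monitor and without a clinical contraindication. Three higher-risk patterns are barred unless a clear non-DILI cause is found. If restart is agreed, "it is recommended that ALT/AST be assessed per protocol schedule of assessments for the first 6 months of the treatment period". The stop rule follows: "The occurrence of new elevation to >3 x ULN for the ALT/AST values will lead to permanent discontinuation of the study drug".

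**Restart in general.** Section 7.1.2.1 makes close monitoring at restart mandatory. It may be clinical, laboratory or both, and no test, interval or duration is named.

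**Testing off drug.** After discontinuation, Appendix 6 says: "Monitor closely (every 2-3 days) until ALT is down-trending, then weekly until <1.5 x ULN, and then at every scheduled visit".

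**The SoA.** Section 8 states: "Adherence to the study design requirements, including those specified in the SoA (Section 1.3), is essential and required for study conduct". Footnote k of Section 1.3 says "Monthly visits (M1, M2, M4, and M5) will include hematology and full liver panel only", and footnote l says "At intermediate timepoints (W2, W3, W5, W6, W7, W9, W10, W11, M7, M8, M10, and M11), only liver function tests will be collected". With the quarterly biochemistry, liver tests fall weekly from Week 2 to Week 12, monthly to Month 12, and quarterly after that.

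**Missed tests.** After one missed timepoint, Appendix 6 tells the site to "inform the study participant that IMP will need to be interrupted if LFTs cannot be monitored as required". After two in a row, drug is held if the participant declines or misses the rescheduled test.

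**Dose-anchored schedules elsewhere.** On a switch to open-label drug, Section 6.6.1 says "he/she will need to be monitored for liver function tests after the first open-label dose", weekly from Week 2 to Week 12 and then monthly for 9 months. Section 10.8.5 requires the same of US participants who stopped within 60 days because of the partial clinical hold and are restarting.

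**The concern.** Severe DILI is an identified risk of this drug (Section 2.3). A participant restarting after an ALT event has already had an ALT rise on study, yet this restart has the softest testing language among the exposure starts that the protocol addresses.

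The permanent-stop rule after rechallenge can act only on a blood result. If a site does only what is required, the date of that result depends on where the participant stands in his or her own SoA, not on when drug was restarted. Off-drug weekly testing does not close the gap: it ends at the same ALT level at which restart becomes possible. Whether the missed-test rules apply to a recommended timepoint is not stated.

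**Working it through.** The plan gives no figure to reproduce, so the check is a count of scheduled tests.

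**Inputs**
- A month is 28 days (Section 4.1), so 6 months is 24 weeks.
- Own SoA liver tests, in weeks from first dose (Section 1.3 and footnotes k and l): 2 to 12 weekly; 16, 20, 24, 28, 32, 36, 40, 44, 48; then 60, 72 and every 12 weeks.
- Restart grid, the same schedule counted from restart week r: r+2 to r+12 weekly (11 tests), then r+16, r+20 and r+24 (14 in total).
- Assumptions: nominal dates, restart at a whole month, own SoA continuing from first dose.

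**Method**
- Required tests in 12 weeks = own-SoA weeks w with r < w ≤ r+12.
- Tests left to the recommendation = grid weeks that are not own-SoA weeks.
- First required test = smallest own-SoA week above r, minus r.

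**Examples**
- Restart at Month 1 (r = 4): own tests up to Week 16 are Weeks 5 to 12 and 16, which is 9. The grid is Weeks 6 to 16, of which Weeks 6 to 12 and 16 (8) are already required. That leaves 11 − 8 = 3 (Weeks 13 to 15).
- Restart at Month 3 (r = 12): own tests are Weeks 16, 20 and 24. The grid is Weeks 14 to 24. That leaves 11 − 3 = 8, and the first required test is at 16 − 12 = 4 weeks.
- Restart at Month 12 (r = 48): the only own test is Week 60. That leaves 11 − 1 = 10, and the first required test is at 60 − 48 = 12 weeks.

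| Restart | Required tests, next 12 weeks | Of these, on the 11-test grid | Left to recommendation, 12 weeks | Left to recommendation, to Month 6 (of 14) | First required test |
|---|---|---|---|---|---|
| Month 1 | 9 | 8 | 3 | 3 | 1 week |
| Month 2 | 6 | 5 | 6 | 6 | 1 week |
| Months 3–6 | 3 | 3 | 8 | 8 | 4 weeks |
| Month 7 | 3 | 3 | 8 | 9 | 4 weeks |
| Months 8–9 | 3 | 3 | 8 | 10 | 4 weeks |
| Month 10 | 2 | 2 | 9 | 11 | 4 weeks |
| Month 11 | 1 | 1 | 10 | 12 | 4 weeks |
| Month 12 on | 1 | 1 | 10 | 12 | 12 weeks at a quarterly visit; 8 or 4 weeks if restart is 1 or 2 months after one |

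The restart grid and the schedules in Sections 6.6.1 and 10.8.5 have their first test at 2 weeks.

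**Anchor.** Section 9.4.5 starts the treatment epoch, for analysis, at the first administration. If the 6 months in the rechallenge sentence ran from that date, own tests remaining inside them would number 7 for a restart at Week 8, 3 at Week 12, 2 at Week 16 and none from Week 24. A recommendation that is empty from Month 6 on can hardly be intended, so the sensible reading is a fresh run from the restart dose. The text does not say so.

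**The case against.** **Appendix 6 calls ALT actions required.** Both its opening and the lead-in to the step list do. But the list grades its own items, some mandatory, some to be considered and some recommended, and the restart sentence uses the softer word. The general heading does not override it.

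**The anchor is a matter of wording.** Largely conceded. On the sensible reading the right tests are named, so what remains in substance is their status.

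**Rechallenged participants are selected.** Section 7.1.2.1 allows restart only if the Investigator judges drug responsibility unlikely and sees no safety concern, and Appendix 6 adds the gates described above. A softer rule for such a group is defensible. The gates decide who restarts, though, not when blood is next drawn.

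**There are other safeguards.** Clinically significant abnormal values should be repeated until they settle (Section 8.2.4). ALT above 3 x ULN is an AESI with proactive follow-up (Sections 8.3.3 and 8.3.9). Independent hepatologists review all potential DILI cases (Section 10.1.5.5). These are real but partial: none sets a date for the next test.

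**The comparators differ.** This stands. Initial start and a switch that may be a first exposure are not re-exposure, and the US hold restart was not prompted by an ALT event. They show that the protocol can write a required, dose-anchored schedule, not that the risk is the same.

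**The missed-test triggers refer to any missed monitoring timepoint.** That is arguable. The interruption message speaks of monitoring as required, and the text leaves recommended timepoints unsettled.

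A reader might infer that no liver testing is required after restart, or that the Months 1 to 3 period for DILI applies again after it. The documents support neither. Own SoA tests continue under Section 8, and Section 2.3 gives that timing only for events after the start of the drug.

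**Conclusion.** The gap is real and limited. After an agreed restart following an ALT event, intensified liver testing is recommended rather than required and is not tied to the restart dose, and the mandatory close monitoring in Section 7.1.2.1 has no schedule.

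For restarts at Months 1 and 2 the effect is small, because a required test comes at 1 week. For Months 3 to 11 the first required test is at 4 weeks, 2 weeks later than on the restart grid. From Month 12 it is at up to 12 weeks, up to 10 weeks later. At a site that does only the required tests, the permanent-stop rule could act late by about that much.

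This rests on nominal dates, on a participant who continues the SoA from first dose, and on the readable text. The ALT flowchart and the Study Manual were not available and may settle the point. The number of restarts is not stated and may be very small. It would go too far to conclude that participants are left unmonitored or that harm is likely. The change is a cheap improvement of low-to-moderate priority.

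**What to change.** Replace the recommendation in the rechallenge item of Appendix 6 with a requirement along these lines: after an agreed restart following an ALT event, liver tests are required on the SoA liver-test schedule, weekly from Week 2 to Week 12 and then at Months 4, 5 and 6, counted from the restart dose; the missed-timepoint rules of this Appendix, including the hold on study drug, apply. If the flowchart or Study Manual already says this, a cross-reference is enough.

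The cost is one sentence. There are no extra panels where sites already follow the recommendation from restart. Elsewhere there are 3 to 12 extra panels per rechallenged participant, depending on the restart month (table above), through the existing central, local or home-nursing routes. Some participants who miss tests would have study drug held. No extension beyond Month 6 is proposed, and sample size and efficacy analyses are unaffected.

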10.8 APPENDIX 8: COUNTRY-SPECIFIC REQUIREMENTS

10.8.1 Contraception requirements in UK, Germany, and Denmark

For inclusion criterion I 09, the following apply:

- For UK and Germany Only: Acceptable forms of effective contraception include the following:
 - Established use of oral, injectable, or implantable progestogen-only hormonal contraception associated with inhibition of ovulation;
 - Placement of an intrauterine device (IUD) or intrauterine hormone-releasing system (IUS);
 - Bilateral tubal occlusion;
 - Male sterilization (provided that the partner is the sole sexual partner of the WOCBP study participant and that the sterilized partner has received medical assessment of the surgical success);
 - True abstinence: When this is in line with the preferred and usual lifestyle of the participant (Periodic abstinence [eg, calendar, ovulation, symptothermal, post-ovulation methods] and withdrawal are not acceptable methods of contraception).
- For Denmark Only: Acceptable methods of effective contraception include the following:
 - IUD;
 - Hormonal contraceptives (contraceptive pills, implants, transdermal patches, hormonal vaginal devices, or injections with prolonged release).

